1 PURPOSE

The purpose of this study is to evaluate the efficacy and safety of the Secret RF device.

2 BACKGROUND INFORMATION

"The use of radiofrequency (RF) microneedling systems in aesthetic medicine has grown substantially. The technology has been widely used for wrinkles, cutaneous ptosis, the treatment of acne scars, skin tightening and stretch marks, among other treatment possibilities"¹.

Fractional Intradermal Radiofrequency (FIRF) delivers superfine needles into the middle layer of the skin and activates radiofrequency energy to tighten and remodel collagen. FIRF uses non-laser radiofrequency technology delivered to the dermis without damaging the top layer of the skin. Micro-needle penetration depth can be adjusted from 0.5 to 3.5mm to tailor the treatment to various thickness of the skin and skin irregularities. The advantage is effective treatment with minimal recovery time.

3 STUDY OBJECTIVES

The objectives of this study are to evaluate the efficacy and safety of the Secret RF device.

4 STUDY DESIGN

This is a multi-center, study in approximately 50 subjects, age 18 and older. . Subjects may receive [REDACTED] treatments and will be followed at 4 and 12 weeks post the final treatment. [REDACTED]

4.1 Study Endpoints

4.1.1 Efficacy Endpoints

- Efficacy of treatments with Cutera's Secret RF as assessed by the investigator for the treatment of improvement in skin quality.
- [REDACTED]

4.1.2 Safety Endpoints

- Incidence and severity of adverse device events.

4.1.3 [REDACTED]

4.2 Study Duration

Subjects enrolled in this trial will be asked to participate for approximately 8 months, depending on treatment(s).

4.3 Study Assessments

4.3.1 Efficacy Assessments

At baseline, and starting at the follow up visits, the Investigator will assess the efficacy of the Cutera Secret RF treatment using the GAIS, [REDACTED] Baseline photos of subjects may be used while assessing the GAIS, [REDACTED]
[REDACTED]

Global Aesthetic Improvement Scale (GAIS): [Only performed after treatment]

[figure not shown]
4 = Very Significant Improvement ($\geq 75\%$)

3 = Significant Improvement (50 – 74%)

2 = Moderate Improvement (25 – 49%)

1 = Mild Improvement (6 – 24%)

0 = No Change ($< 5\%$)

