5.1.1 Inclusion Criteria

To be included in the study, subjects must meet all of the following Inclusion Criteria:

1. Subject must be able to read, understand and sign the Informed Consent Form.
2. Female or Male, age 18 and older.
3. Willing to undergo treatments with Secret RF.
4. Willing to have very limited sun exposure and use sunscreen on the treatment area every day for the duration of the study, including the follow-up period.
5. Subject must adhere to the follow-up schedule and study instructions.
6. Agree to not undergo any other cosmetic procedure(s) or treatment(s) on the treatment area during the study and has no intention of having such procedures performed during the course of the study.
7. Willing to have digital photographs taken of the treatment area and agree to use of photographs for presentation, (educational and/or marketing), publications, and any additional marketing purposes.
8. For female subjects: not pregnant or lactating and is either post-menopausal, surgically sterilized, or using a medically acceptable form of birth control prior to enrollment and during the entire course of the study.

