7.2 Recording AEs/ADEs and SAEs/SADEs

All AEs/SAEs or ADEs/SADEs will be: (1) evaluated and must be recorded in the subject's study case report forms (CRFs); (2) monitored and tracked from the time of the first treatment.

At each contact with the subject, the investigator must seek information on AEs/ADEs/SADEs by specific questioning and, as appropriate, by examination. AEs/ADEs/SADEs may be observed by the investigator and/or clinical research staff, elicited from the subject and/or family member or volunteered by the subject. All observed and volunteered adverse signs and symptoms, anticipated or unanticipated, regardless of severity or frequency, will be recorded in the case histories (medical chart and CRFs). Included in the description should be the nature of the sign or symptom, the date of onset, date of resolution (duration), the severity, anticipated or unanticipated, the relationship to study treatment or other therapy, the action taken (if any), and the outcome. All SAEs/SADEs, anticipated or unanticipated, must be reported to Cutera immediately but not later than 5 working days. The SADE must be recorded in: (1) the CRF and (2) a written report must be submitted to Cutera within five (5) working days after the investigator first learns of the event and is to include a full description of the event and sequelae, in the format detailed by the Cutera Serious Adverse Event Form.

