9.3 Analysis of Efficacy/Exploratory Endpoints

Formal hypothesis testing and statistical analysis are not planned for this study.

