9.4 Safety Analyses

Device-related and procedure-related adverse effects (AEs) will be tabulated and analyzed. For a given AE term, counting will be done by subject, not by event, i.e. for a subject reporting the same AE more than once, the event will be counted only once, at the most severe and longest duration. The number and percentage of subjects experiencing each AE Term will be descriptively summarized.

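### The GAIS as printed has no level for worsening, so on its own it cannot count subjects who look worse, and its mean cannot fall below zero

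*Protocol*

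**What the plan says.** The readable efficacy endpoint in section 4.1.1 is the investigator's assessment of improvement in skin quality. The GAIS is the only instrument for it that can be read in section 4.3.1; others may be redacted.

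The scale is headed "Global Aesthetic Improvement Scale (GAIS): [Only performed after treatment". Its levels are 4 (75% or more), 3 (50–74%), 2 (25–49%), 1 (6–24%, "1 = Mild Improvement") and 0 (no change, under 5%). Nothing is printed below 0. Section 4.3.2 follows directly, with no redaction or figure mark between. The one missing figure stands above level 4.

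Other relevant text:
- Section 4.3.1 also speaks of assessment "At baseline, and starting at the follow up visits" and says "Baseline photos of subjects may be used while assessing the GAIS".
- Section 5.1.1 requires subjects to be "Willing to have digital photographs taken of the treatment area".
- Section 7.2 states "All observed and volunteered adverse signs and symptoms, anticipated or unanticipated, regardless of severity or frequency, will be recorded in the case histories".
- Section 9.3 states "Formal hypothesis testing and statistical analysis are not planned for this study".
- Section 9.4 states "Device-related and procedure-related adverse effects (AEs) will be tabulated and analyzed".

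**The concern.** The scale grades change in one direction only, and the text does not say whether the under-5% limit on level 0 is signed.

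- **Signed:** a subject who looks worse scores 0, together with everyone who did not change.
- **Size of change:** a subject who looks clearly worse fits no level, and the rater must leave the item blank or improvise.

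Investigators at different centers could resolve this differently. An improvement of exactly 5% also falls between levels 0 and 1, which is a minor gap.

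No control group is described in the readable text and no formal testing is planned, so the distribution of scores is itself the visible efficacy result. If every subject looked worse, the signed reading would report 100% no change and a mean of 0. An analysis plan cannot repair this, because the category is never collected.

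**Working it through.** The protocol gives no effect size, rating variability or expected rate of worsening, so there is no figure of its own to reproduce. The inputs are the printed levels (section 4.3.1) and the sample sizes of about 50 (section 4) and 40 (section 9.1). Everything else is labelled as an assumption.

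**1. Range of the score.** The codes are 0, 1, 2, 3 and 4, so any mean lies between 0 and 4.

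**2. Worse subjects scored 0.** Compared with a scale that has a −1 level, each worse subject adds 1 point to the total, so

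mean(worse = 0) − mean(worse = −1) = w/n.

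With 5 of 50 or 4 of 40 worse, the difference is 0.10. With 10 of 50 or 8 of 40 it is 0.20. This needs no model. Percent improved (score 1 or more, out of all assessed) is the same on both scales.

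**3. Worse subjects left blank and dropped.** Percent improved becomes x/(n − w).
- Assumed 30 of 50 improved and 5 worse: 30/50 = 60.0% becomes 30/45 = 66.7%.
- Assumed 24 of 40 improved and 4 worse: 24/40 = 60.0% becomes 24/36 = 66.7%.

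**4. Dependence on the true effect.** Assume the rated change is Normal around a common true change, with SD 10 percentage points (range 5 to 20). Use cuts at 5.5, 24.5, 49.5 and 74.5%, and call a subject worse below −5.5%. The mean score with worse = 0 is the sum of the probabilities of exceeding each cut. The mean with a −1 level subtracts P(worse).

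For a true change of 0 and SD 10, P(above 5.5) = 0.291, P(above 24.5) = 0.007 and P(worse) = 0.291. The means are therefore 0.298 and 0.298 − 0.291 = 0.007.

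| True change | Mean, worse = 0 (SD 10) | Mean with −1 level (SD 10) | Difference (SD 10) | Difference, SD 5 to 20 |
|---|---|---|---|---|
| 0 | 0.298 | 0.007 | 0.291 | 0.136 to 0.392 |
| +10% | 0.747 | 0.687 | 0.061 | 0.001 to 0.219 |
| +25% | 1.501 | 1.500 | 0.001 | 0.000 to 0.064 |

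If worse subjects are instead dropped, percent improved at SD 10 moves from 29.1% to 41.1% (true change 0), from 67.4% to 71.7% (+10%) and from 97.4% to 97.6% (+25%).

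**5. What a worse level would allow.** With no worse subjects observed, the exact two-sided 95% upper limit for the worsening rate is 1 − 0.025^(1/n). That is 7.1% for n = 50 and 8.8% for n = 40. The printed GAIS alone gives no such bound, because a count of zero worse cannot be observed on it.

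**The case against.** The case on the other side has five parts.

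- **No mean is planned.** The readable text proposes no GAIS mean, and how scores are summarized may be set elsewhere. This is true. The statement about the mean describes a property of the scale, not an announced analysis. The loss of the worse count remains under any summary.
- **The signed reading is the natural one**, since the other levels are signed improvement, and percent improved is then unaffected. This also stands. The 66.7% figures need both the other reading and dropped blanks, and no section says blanks would be dropped. Worse and unchanged subjects still share one code.
- **The modelled sizes rest on an assumed SD.** They do, and the largest difference arises only if the device has no effect. They show when the defect matters, not what will happen.
- **Other routes exist.** Section 4.3.1 mentions baseline assessment although the GAIS is done only after treatment, so a redacted instrument could show worsening as change from baseline. A second efficacy item, section 4.1.3, the section 6 procedures and later pages are also redacted and could hold scoring instructions. Photographs and adverse event records may identify some worsened subjects. However, adverse events are graded by interference with activity and need for treatment, which is not an aesthetic rating, and nothing readable feeds any of these sources back into the GAIS score.
- **An improvement-only scale suits an improvement endpoint.** It is a design choice and not a contradiction. In an uncontrolled descriptive study, though, it leaves out the outcome a reader would want beside the improvements.

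**Conclusion.** The concern holds for the GAIS as printed and taken alone. It cannot show how many subjects look worse, and its mean is bounded below by zero. That a level is missing from the printed list is near certain, since the list descends to 0 and the next section follows without a gap.

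The practical size is unknown. A mean would be too high by the proportion worse if those subjects score 0. Percent improved would be inflated only if they are left blank and excluded. On the assumed Normal model, the bias in the mean is material when the true effect is near zero and negligible at a 25% improvement with SD 10. No hypothesis test is affected. This is an inexpensive improvement that should be made, not a flaw that invalidates the study.

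**What to change.** In section 4.3.1 and on the form used to record the GAIS, use contiguous bands:

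- −1: worse, by 5% or more
- 0: no change, less than 5% in either direction
- 1: improvement of 5% to under 25%
- 2: 25% to under 50%
- 3: 50% to under 75%
- 4: 75% or more

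Report the number and percentage at every level, including worse, at the 4- and 12-week visits.

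The cost is one added level and reworded bands; the form itself is not shown. The summary may look slightly less favorable and will differ from a 0–4 version. Under the signed reading, collapsing −1 into 0 recovers the printed score apart from the previously uncoded 5%. Under the size-of-change reading it does not, because worse subjects had no code before. One negative level against four positive ones reduces the asymmetry without removing it: with no true change, SD 20 and the cuts used above, the mean is still +0.12. The count of worse subjects should therefore be reported in its own right and not only through a mean.

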4.3.2 Safety Assessments

Following the first treatment, adverse events (AEs) will be assessed post-treatment and at each subsequent visit using the following scale:

- 1= mild: requires minimal or no treatment and does not interfere with the subject's daily activities.
- 2= moderate: may cause some interference with functioning.
- 3= severe: interrupts subject's usual daily activity and may require treatment.

Treatment-related Discomfort:

After each treatment, subjects will be asked to rate the average amount of discomfort experienced during treatment and immediately after treatment using the Pain Rating Scale (VAS Scale) Appendix 2.

4.4 Study Discontinuation

Cutera, Inc. (the sponsor) has the right to terminate this study at any time. Reasons for terminating the study may include, but are not limited to, the following: incidence or severity of adverse events in this or other studies indicates a potential health hazard to subjects; subject enrollment is unsatisfactory; number of protocol deviations is unacceptable; data recording is inaccurate or incomplete; or questionable study site compliance with ICH-E6, Good Clinical Practice.

4.5 Investigator Selection

The Investigator(s) will be invited to participate in the study based on his or her medical specialty, experience conducting clinical research studies and experience in the use of microneedle RF devices for aesthetic indications. Access to potential study subjects and the Investigator's sincere interest in this study along with expressed willingness to cooperate with the study process and requirements are also considered.

5 STUDY POPULATION

5.1 Study Subject Recruitment and Selection

Approximately 50 male or female subjects, age 18 and older., with Fitzpatrick Skin Type I-VI who desire treatment with Secret RF. Subjects will be recruited to participate from the local population. Subjects may also be recruited from the Investigator's existing patient database or from patients who present themselves to the study site requesting treatment. Only subjects who meet all eligibility criteria and who provide written informed consent will be enrolled into the study.

Each subject will be evaluated by the Investigator to assess his/her suitability for entry into the study according to the following inclusion and exclusion criteria.

5.1.1 Inclusion Criteria

To be included in the study, subjects must meet all of the following Inclusion Criteria:

1. Subject must be able to read, understand and sign the Informed Consent Form.
2. Female or Male, age 18 and older.
3. Willing to undergo treatments with Secret RF.
4. Willing to have very limited sun exposure and use sunscreen on the treatment area every day for the duration of the study, including the follow-up period.
5. Subject must adhere to the follow-up schedule and study instructions.
6. Agree to not undergo any other cosmetic procedure(s) or treatment(s) on the treatment area during the study and has no intention of having such procedures performed during the course of the study.
7. Willing to have digital photographs taken of the treatment area and agree to use of photographs for presentation, (educational and/or marketing), publications, and any additional marketing purposes.
8. For female subjects: not pregnant or lactating and is either post-menopausal, surgically sterilized, or using a medically acceptable form of birth control prior to enrollment and during the entire course of the study.

5.1.2 Exclusion Criteria

Subjects will be excluded from the study if they meet any of the following Exclusion Criteria:

1.	Participation in a clinical trial of another device or drug within 1 month of study participation, or during the study period.
----	--

2.	History of clotting disorders and/or current use of blood thinning medications.
3.	History of autoimmune disorders or diabetes.
4.	Cardiac pacemaker or active implantable metal device in the treatment area.
5.	Allergies to metals i.e. gold.
6.	Has a history of squamous cell carcinoma or melanoma in the treatment area.
7.	Significant uncontrolled concurrent illness that in the opinion of the Investigator would make the subject unsuitable for inclusion.
8.	History of any disease or condition that could impair wound healing.
9.	History of keloid formation or abnormal/delayed wound healing.
10.	History of disease stimulated by heat, such as recurrent herpes simplex and/or herpes zoster (shingles) in the treatment area, unless treatment is conducted following a prophylactic regimen.
11.	Use of topical agents one week prior to treatment that may cause facial sensitivity.
12.	Suffering from significant skin conditions in the treated areas or inflammatory skin conditions, including but not limited to, open lacerations or abrasions, hidradenitis, rash, infection, or dermatitis of the treatment area prior to treatment (duration of resolution as per the Investigator's discretion).
13.	As per the Investigator's discretion, any physical or mental condition which might make it unsafe for the subject to participate in this study or a condition that would compromise the subject's ability to comply with the study requirements.

5.2 Subject Numbering

If a subject completes the Informed Consent Form, meets the study eligibility criteria and is willing to participate, the subject will be assigned a study subject identification number. This number is comprised of a site number (which is provided by the sponsor) and a sequential subject number and the subject initials (first and last names).

5.2.1 Subject Discontinuation Criteria

If possible, every subject should remain in the study until completion of the required follow-up period. However, participation in this study is completely voluntary and a subject can choose to withdraw from the study at any time. Decision to withdraw will not affect or prejudice the subject's continued medical care in any way. In those instances, the investigator will attempt to obtain a final clinical assessment and an adverse device effect evaluation for the subject prior to this withdrawal. A subject will be considered lost to follow-up only after three unsuccessful, documented attempts to contact the subject have been made.

In addition, a subject can be discontinued for any of the following reasons: the Principal Investigator decides that continuing in the study would not be in the subject's best interest, a subject is noncompliant with the protocol, a subject has a serious reaction to the treatment, a subject develops any of the exclusion criteria during the study period or the study is stopped by the study sponsor.

[REDACTED]

[REDACTED]

[REDACTED]

7 ADVERSE EVENTS AND ADVERSE DEVICE EVENTS

[REDACTED]

[REDACTED]

[REDACTED]

[REDACTED]

[REDACTED]

[REDACTED]

[REDACTED]

[REDACTED]

[REDACTED]

[REDACTED]

[REDACTED]

[REDACTED]

[REDACTED]

7.2 Recording AEs/ADEs and SAEs/SADEs

All AEs/SAEs or ADEs/SADEs will be: (1) evaluated and must be recorded in the subject's study case report forms (CRFs); (2) monitored and tracked from the time of the first treatment.

At each contact with the subject, the investigator must seek information on AEs/ADEs/SADEs by specific questioning and, as appropriate, by examination. AEs/ADEs/SADEs may be observed by the investigator and/or clinical research staff, elicited from the subject and/or family member or volunteered by the subject. All observed and volunteered adverse signs and symptoms, anticipated or unanticipated, regardless of severity or frequency, will be recorded in the case histories (medical chart and CRFs). Included in the description should be the nature of the sign or symptom, the date of onset, date of resolution (duration), the severity, anticipated or unanticipated, the relationship to study treatment or other therapy, the action taken (if any), and the outcome. All SAEs/SADEs, anticipated or unanticipated, must be reported to Cutera immediately but not later than 5 working days. The SADE must be recorded in: (1) the CRF and (2) a written report must be submitted to Cutera within five (5) working days after the investigator first learns of the event and is to include a full description of the event and sequelae, in the format detailed by the Cutera Serious Adverse Event Form.

7.3 Follow-up of Subjects after AEs

All reported AEs/ADEs/SAEs/SADEs should be followed until resolution or until the subject's participation in the study ends. Resolutions of AEs/ADEs/SAEs/SADEs are to be documented on the appropriate CRFs.

[REDACTED]	[REDACTED]	[REDACTED]	[REDACTED]
[REDACTED]	[REDACTED]	[REDACTED]	[REDACTED]
[REDACTED]	[REDACTED]	[REDACTED]	[REDACTED]
[REDACTED]	[REDACTED]		[REDACTED]
[REDACTED]	[REDACTED]		[REDACTED]
[REDACTED]	[REDACTED]		[REDACTED]

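### Section 7.3 ends follow-up of serious and device-related events at the subject's exit, so the final outcome of any such event still open then need not be collected

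*Protocol*

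**What the plan says.** Protocol section 7.3 gives one follow-up rule for AEs, ADEs, SAEs and SADEs alike: they "should be followed until resolution or until the subject's participation in the study ends". No exception for serious or device-related events is visible.

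Section 7.2 lists what is recorded for each event, including "the date of onset, date of resolution (duration), the severity" and "the action taken (if any), and the outcome". Duration is thus tied to having a resolution date.

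Section 9.4 tabulates device- and procedure-related effects by subject. Where a subject reports the same term more than once, "the event will be counted only once, at the most severe and longest duration". The output it names is the number and percentage of subjects per term.

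Section 5.2.1 treats two routes out of the study. For a subject who chooses to withdraw, "the investigator will attempt to obtain a final clinical assessment and an adverse device effect evaluation for the subject prior to this withdrawal". A separate paragraph then lists reasons for which a subject can be discontinued, one of them being that "a subject has a serious reaction to the treatment".

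Under section 4, subjects "will be followed at 4 and 12 weeks post the final treatment". Section 4.2 puts total participation at about 8 months. Section 9.2 restricts the analysis sets to enrolled subjects who complete treatment.

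**The concern.** The follow-up rule is least informative for the events on which one would most want information. An event that clears before exit is documented in full. One that persists to exit, or is serious enough to cause the exit, may be followed no further without any breach of the protocol.

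What is lost is the final outcome. For an event open at exit, the required data cannot show whether it cleared soon afterwards or became permanent. Safety is one of the two study objectives, and the attribute that 9.4 attaches to a repeated event includes its longest duration, so this information has a place in the plan. It also cannot be recovered at the analysis stage: a SAP can label an event as ongoing, but it cannot supply an outcome that nobody was required to collect.

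**Working it through.** The plan gives no figure to reproduce. The check is a reading of the sections together, followed by an illustration.

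**1. What can be observed.** Under 7.3 the observable duration is

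observed = min(true duration, time from onset to end of participation).

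For a completer, with the last visit 12 weeks after the final treatment (section 4):
- onset at the final treatment: at most about 12 weeks;
- onset at the 4-week visit: at most 12 − 4 = about 8 weeks;
- onset early in the study: at most about 8 months (section 4.2).

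For a subject discontinued because of a reaction, the limit is the time from onset to discontinuation, which may be short.

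**2. What the record holds for an event open at exit.** Section 7.2 asks for a resolution date, and there is none. The duration is missing or, if cut at exit, a lower bound. The outcome field can show that the event was unresolved on that date. Nothing visible requires a later entry.

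**3. Whether the exit evaluation fills the gap.** In 5.2.1 it is an attempt, it is made before the withdrawal, and its wording refers back to subjects who choose to leave. Discontinuation for a serious reaction comes in the next paragraph, with no such duty in the visible text. Even when the evaluation is done, one contact before exit cannot show what happened afterwards.

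**4. Whether the subject is tabulated at all.** Read literally, 9.2 excludes a subject who does not complete treatment. A reaction that stops treatment early could then be missing from the 9.4 table altogether. A reaction that leads to exit after the final treatment would stay in the table, with an open duration.

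**5. Illustrative size.** The documents give no event rates or durations. Assume exponential durations with median m weeks, and T weeks from onset to exit. Then

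P(open at exit) = 0.5^(T/m).

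Take T = 10, that is, onset 2 weeks after the final treatment and exit at the 12-week visit:

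| Assumed median m (weeks) | T/m | Open at exit |
|---|---|---|
| 1 | 10 | 0.1% |
| 2 | 5 | 3.1% |
| 4 | 2.5 | 17.7% |
| 8 | 1.25 | 42.0% |
| 16 | 0.625 | 64.8% |

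If participation ends 2 weeks after onset (T = 2), the same formula gives 25%, 50%, 71%, 84% and 92%. The distribution, the medians and both values of T are assumptions. The table shows only how strongly the answer depends on them.

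**6. What does not change.** The safety endpoint in 4.1.2 is incidence and severity of adverse device events, and 9.4 names numbers and percentages of subjects per term. An event recorded before exit counts in these whether or not its end date is known.

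**The case against.** Much of the case on the other side stands. Sections 7.3 and 9.4 can both be followed, so this is not a contradiction. Every study of finite length cuts off some events. The outcome field in 7.2 can already mark an event as unresolved, and a SADE needs a written report covering sequelae, though that report is due within five working days of the investigator first learning of the event. Discontinuation for a serious reaction is permitted, not required, and 5.2.1 asks that subjects stay to the end of follow-up where possible. Much of section 7 before 7.2, the text after 5.2.1 and the material at the end of the protocol are redacted, so the absence of an exception can be asserted only for the visible text. With short-lived effects almost nothing is open at 10 weeks.

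A reader might go further and infer three things that the documents do not support:

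- *That the safety endpoint is biased.* Incidence and severity counts do not depend on when an event ends.
- *That reported durations will be too short by a calculable factor.* The visible text plans no mean-duration summary, and any such factor would rest on an assumed distribution.
- *That 9.4 ranks a resolved episode above a longer open one, or treats an open event as having no duration.* Section 9.4 says neither. How ongoing events are coded and ranked is ordinary SAP detail.

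What survives is narrower. Marking an event as unresolved at exit is not the same as knowing its outcome, and no visible provision requires that outcome to be sought.

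**Conclusion.** The point holds in a limited form. On the visible text, required follow-up of a serious or device-related event stops at exit even if the event is open, and a serious reaction may itself be the reason for exit. The later outcome of such an event need not be collected, and its duration is missing or a lower bound. The stated incidence and severity outputs are not affected.

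Its size cannot be computed from the documents. At 10 weeks from onset to exit, the assumed medians of 1 to 16 weeks span about 0.1% to 65% of events open, so the problem may be negligible or substantial. The conclusion assumes that no redacted passage extends follow-up. It is a cheap improvement to data collection in a descriptive study, and it does not threaten the study's main safety counts.

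**What to change.** Reconcile 7.3 with 5.2.1, 7.2, 9.2 and 9.4:

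- **7.3:** for device- or procedure-related AEs and for SAEs/SADEs open at exit, whether at the 12-week visit or at early discontinuation, continue to collect outcome data by telephone or chart contact. The sponsor and investigator should set and state the end point of that follow-up.
- **5.2.1:** state whether the exit evaluation also applies to subjects discontinued by the investigator or sponsor, including for a reaction.
- **9.4 (or the SAP):** report the number of subjects with such an event unresolved at last contact, and show its duration as at least x, measured to that contact.
- **9.2:** make sure that subjects discontinued for a reaction are not dropped from the safety tabulation.

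The cost is a few sentences, a few extra contacts for subjects with an open related or serious event, and somewhat later final safety data.
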